11.5.6.1 Analysis of endpoint

The proportion of infants with WAZ > -2 at Day 56 with 95% CIs will be estimated and presented in a table by treatment group. The binomial mid-P method will be used to estimate the CIs.

Log-binomial regression will be used to estimate the risk ratio of WAZ > -2 rates at Day 56 between Bi-26 and Placebo, adjusting for the following covariates: baseline WAZ, age (in days), country and discharge destination. The adjusted risk ratio (exponentiated coefficient) with 95% CI will also be presented in the same summary table as the proportion estimates. If the overall rate is less than 15% of all participants or the log-binomial model does not converge, then logistic regression will be used in the place of log-binomial regression and odds ratios will be reported instead of risk ratios, which will be a reasonable estimate of the risk ratios. PROC GLIMMIX will be used for this analysis.

The Safety and PP populations will be used for this analysis.

Increases will be indicated as flags in the WAZ listing described in Section 11.5.2.1.

11.5.7 Re-hospitalization rates through Day 56

The number of re-hospitalizations for acute non-surgical illness by Day 56 per participant will be summarized using descriptive statistics and will be presented in a table by treatment group.

Negative-binomial regression will be used to estimate the incidence rate ratio of re-hospitalization at Day 56 between Bi-26 and Placebo, adjusting for the following covariates: baseline WAZ, age (in days), country and discharge destination. The adjusted rate ratio (exponentiated coefficient) with 95% CI will also be presented in the same summary table as the descriptive statistics.

The number and proportion of infants that were re-hospitalized for acute non-surgical illness by Day 56 with 95% CIs will be presented in a table by treatment group. The binomial mid-P method will be used to estimate the CIs.

Log-binomial regression will be used to estimate the risk ratio of re-hospitalization rates at Day 56 between Bi-26 and Placebo, adjusting for covariates baseline WAZ, age (in days), country and discharge destination. The adjusted risk ratio (exponentiated coefficient) with 95% CI will also be presented in the same summary table. If the overall re-hospitalization rate is less than 15% of all participants or the log-binomial model does not converge, then logistic regression will be used in the place of log-binomial regression. Odds ratios will be reported instead of risk ratios, which will be a reasonable estimate of the risk ratios.

PROC GLIMMIX will be used for this analysis.

Confidential Page 36 of 50

Re-hospitalizations for acute non-surgical illness will be listed in a separate listing for all participants, including date/time of admission, associated SAE, preferred term of SAE and date/time of discharge if discharged.

The Safety and PP populations will be used for this analysis.

11.5.7.1 Subgroup analysis

The number and proportion with 90% CIs of infants that were re-hospitalized for acute non-surgical illness by Day 56 may be presented in a table by treatment group for subgroups as specified in Section 8.2. The binomial mid-P method will be used to estimate the CIs. Results will be presented for the mITT population.

11.5.8 Presence of *B. infantis* in stool

The proportion of infants with presence of *B. infantis* with 95% CIs will be estimated and presented in a table by treatment group for Days 1, 28, 56, and 90. The binomial mid-P method will be used to estimate the CIs. The definition of "presence of *B. infantis*" will be refined following qPCR validation activities in which a threshold for presence/absence will be determined.

A listing will be provided including date of sample collection, Bristol stool scale, fecal pH, and presence of *B. infantis*.

The mITT and PP populations will be used for this analysis.

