| Objectives | Endpoints |
|---------------------------------------------------------------------------------------------------------|---------------------------------------------------------------------------------------------------------------------------|
| Primary | |
| To evaluate the change in weight (standardized for age) of infants receiving Bi-26 | WAZ change from baseline (Day 1) to the Day 56 visit in Bi-26 group |
| Key Secondary | |
| To evaluate the change in weight of infants receiving Bi-26 | Change in weight (in grams) from baseline (Day 1) to the Day 56 visit in the Bi-26 group |
| Other Secondary | |
| To estimate the treatment response over time associated with Bi-26 | WAZ change from baseline (Day 1) over time through the Day 90 visit (longitudinal assessment) by duration of dosing |
| To assess the proportion of infants who achieve a specified change in WAZ from baseline to Day 56 | Proportion of infants with $a \ge 0.3, \ge 0.4$, and ≥ 0.5 change in WAZ from baseline (Day 1) to Day 56 visit |
| To assess the proportion of infants who achieve a specified WAZ at Day 56 | Proportion of infants who achieve a WAZ > -2 at Day 56 visit |
| To assess the re-hospitalization rate | Number of re-hospitalizations for acute non-surgical illness through the Day 56 visit |
| To assess the safety of Bi-26 supplementation through End of Study (EoS, Day 90 visit) | Number of adverse events (AEs) and serious adverse events (SAEs) through Day 90 |
| To measure engraftment of B. infantis in participants | Presence of B. infantis in stool on Days 1, 28, 56, and 90 |

| Objectives | Endpoints |
|------------------------------------------------------------------------------------------------------------------------------|----------------------------------------|
| Exploratory | |
| To describe stool biomarkers in response to Bi-26 supplementation in terms of stool composition (e.g., microbiome, pH) | Stool biomarkers on Days 1, 28, and 56 |
| To describe the blood biomarkers (e.g., inflammation, metabolomics), in response to Bi-26 supplementation | Blood biomarkers on Days 1 and 28 |

Table 2: Schedule of Activities (SoA)

| Activities | | Clinic Visit 1 | | Homo Visits | e 5 | Clinic Visit 2 | Home Visit | Home Visit | Home Visit | Clinic Visit 3 | Clinic Visit 4 | Discon Visit ^b |

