Bifidobacterium longum subspecies infantis (*B. infantis*) is a commensal bacterial strain common in the microbiome of breast-fed infants younger than 6 months of age in LMICs that has the unique ability to efficiently process HMOs. Although breast-feeding support is a key part of treatment of malnourished infants, this alone may be insufficient to support recovery. A decrease in abundance or absence of *B. infantis* could lead to inadequate HMO processing, elevating intestinal pH and increasing the risk of pathogen overgrowth. Intervention with a *B. infantis* probiotic strain such as Bi-26, in vulnerable malnourished infants could have a significant shortterm impact on nutritional recovery and mortality, and long-term impact on health and development outcomes by potentially breaking the cycle of impaired immunity, recurrent infections, and worsening malnutrition.

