4.3. Justification for Dose

The primary goal of this study is to confirm the findings of the initial study in Bangladesh (SYNERGIE study) in which 4 weeks of single daily feeding with *B. infantis* EVC001 resulted in significant weight gain relative to placebo, and in *B. infantis* colonization for at least 4 weeks post end of treatment. The target dose listed in the SYNERGIE study was approximately 8 billion CFUs with a 28-day duration of treatment; however, the amount of product initially packaged, and the potential range of doses administered over the course of the study was not provided [Barratt 2022]).

CFU per dose included in this study is expected be generally comparable to that in the SYNERGIE study. Refer to the Gates MRI IB addendum for additional information.

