5.1. Inclusion Criteria

Participants are eligible to be included in the study only if all of the following criteria apply:

Age

1. Participant must be between 30 days and 120 days of age (inclusive), at the time of enrollment (study Day 1)

Type of Participant and Disease Characteristics

- 2. Hospitalized for acute non-surgical illness
- 3. Completed acute stabilization phase of treatment, including fluid rehydration and antibiotic course, prior to enrollment (study Day 1)

Weight

4. WAZ at enrollment (study Day 1) is less than negative 2 (<-2)

Sex

5. Any

Informed consent

6. Participant's parent(s)/legal guardian is capable of giving informed consent which includes agreement to comply with the requirements and restrictions listed in the informed consent form (ICF) and in this protocol

Additional requirements

- 7. Participant's parent(s)/legal guardian agrees to stay in contact with the study site for the duration of the study, provide updated contact information as necessary, and have no current plans to relocate from the study area for the duration of the study
- 8. Participant's parent(s)/legal guardian has easy access to reliable refrigeration (for storage of investigational product)
- 9. Participant receives some feedings from breastmilk and mother intends to continue breast-feeding.

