8.6. Biomarkers

To assess the biomarker study endpoints, serum and stool samples will be collected from all infants for biomarker research. All of these samples, or a subset of these samples from a representative cohort of all participants, may be tested to identify analytes of interest.

At Visit 1 Day 1 and Visit 2 Day 28, as indicated in the SoA (Table 2), a blood sample will be collected and processed to serum from all participants. Restricted blood volumes may be dependent on the physician discretion and/or the participant's health/condition. Testing will be determined by the amount of available blood collected.

These serum samples will be tested for biomarkers including, but not limited to, host inflammatory biomarkers and metabolic analysis. No host genetic analyses will be performed.

The maximum amount of blood collected from each participant over the duration of the study will not exceed approximately 4 mL.

Repeat or unscheduled samples may be taken for safety reasons or for technical issues with the samples.

Stool samples for measurement of exploratory biomarkers will also be collected at clinic visits as specified in the SoA (Table 2), in addition to stool samples collected for the secondary endpoint, (refer to Section 9.7.1). Collection will be performed by trained study team staff at specified clinical visits. Either taking temperature or a rectal swab will be performed to stimulate defecation. Defecation at any time during the clinical visit prior to stool collection can substitute for this rectal swab.

Fecal pH and Bristol or similar stool scale will be measured and recorded by the trained study team staff, at the time of stool collection. Samples will be tested for microbiome composition including levels of total Bi-26 measured by nucleotide sequencing and/or polymerase chain reaction. Stool samples may be tested for biomarkers including, but not limited to, inflammatory biomarkers and host and/or bacterial metabolic analysis.

9. Statistical Considerations

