7.3 Efficacy Measures

The following endpoints will be analyzed for primary efficacy analysis:

• Change in WAZ from baseline to Day 56 visit in the Bi-26 group.

For the secondary endpoints the following will be analyzed:

- Change in weight (in grams) from baseline to Day 56 visit in the Bi-26 group.
- Change in WAZ over time from baseline to Day 90 visit (longitudinal assessment) by duration of dosing.
- Proportion of infants with a $\geq 0.3, \geq 0.4$, and ≥ 0.5 change in WAZ from baseline (Day 1) to Day 56 visit.
- Proportion of infants with WAZ > 2 at Day 56 visit.
- Proportion of re-hospitalizations for acute non-surgical illness through Day 56 visit.
- Presence of *B. infantis* in engraftment stool samples on Days 1, 28, 56, and 90.

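### The engraftment endpoint is reported only as by-arm proportions with B. infantis present; a Day 56 and Day 90 difference from placebo, using Day 1 status, would measure engraftment better from the same samples

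*SAP*

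**What the plan says.** Protocol Table 1 lists a secondary objective that begins "To measure engraftment of" *B. infantis*. SAP 7.3 gives the endpoint as presence of *B. infantis* "in engraftment stool samples on Days 1, 28, 56, and 90".

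Under SAP 11.5.8 the proportion positive "with 95% CIs will be estimated and presented in a table by treatment group for Days 1, 28, 56, and 90", using mid-P intervals, in the mITT and PP populations. The cut-off is still open: the definition of presence "will be refined following qPCR validation activities in which a threshold for presence/absence will be determined". SAP Table 8 lists the same method and nothing more. By contrast, SAP 11.5.5 to 11.5.7 give the WAZ responder and re-hospitalization endpoints an adjusted between-arm ratio with a 95% CI.

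Four other places bear on the reading:

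- Protocol Section 2 says *B. infantis* "is a commensal bacterial strain common in the microbiome of breast-fed infants younger than 6 months of age in LMICs". Inclusion criterion 9 reads "Participant receives some feedings from breastmilk and mother intends to continue breast-feeding".
- Protocol Table 3 describes a matched placebo without *B. infantis*.
- Protocol 4.3 cites the pilot finding of *B. infantis* "colonization for at least 4 weeks post end of treatment" as part of what this trial sets out to confirm.
- Protocol 8.6 adds: "Samples will be tested for microbiome composition including levels of total Bi-26 measured by nucleotide sequencing and/or polymerase chain reaction". That readout is not mentioned in SAP 11.5.8.

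**The concern.** An engraftment result should show that supplementation left *B. infantis* in the gut after dosing stopped. The planned output mixes that with two other sources of a positive stool.

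The first is native carriage. Infants who already carry *B. infantis* can test positive in either arm, whatever the supplement does. The Day 1 sample could identify them, but it is tabulated as one more visit.

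The second is dose passage at Day 28. Dosing is daily for 28 days, and the Schedule of Activities still lists a dose at the Day 28 visit. The footnote requiring samples before dosing is attached to Day 1. Even a Day 28 sample taken before that day's dose would normally follow a dose given about a day earlier. The placebo arm cannot correct for this, because only the Bi-26 arm receives *B. infantis*.

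Engraftment is the proposed mechanism for the weight effect. If the weight result were null, the trial would need to distinguish a product that did not persist from one that persisted without benefit. Day 56 is the visit that speaks to this, yet it is one of four columns of equal standing.

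**Working it through.** **The plan's own figure.** The documents contain no calculation for engraftment. The only design calculation is for WAZ: difference 0.45, SD 1.3, two-sided 5%, 90% power (Protocol 9.4). The normal formula gives 2 × (1.960 + 1.282)² × 1.3² / 0.45² ≈ 175.4, so 176 per arm. The t-test version gives 176.35, so 177, as stated. The 177 is used below only as an illustrative arm size.

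**Time since the last planned dose.** The windows come from SAP Table 4, and the last planned dose is on Day 28.

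| Visit | Window | Days after last planned dose |
|---|---|---|
| Day 28 | 27 to 29 | −1 to +1 |
| Day 56 | 54 to 58 | 26 to 30 |
| Day 90 | 88 to 92 | 60 to 64 |

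For an infant who completes dosing on schedule, Day 28 cannot separate passage from engraftment. At Days 56 and 90 the planned doses do not explain a positive sample. Day 56 also matches the pilot's interval of about 4 weeks.

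**Native carriage at Day 56 or Day 90.** Let p be native carriage and e the Bi-26 engraftment rate, independent of each other. Both are assumptions; the documents give no value for either.

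- Placebo-arm proportion = p
- Bi-26-arm proportion = p + (1 − p)e
- Difference = (1 − p)e
- Share of Bi-26-arm positives without Bi-26 = p(1 − e) / [p + (1 − p)e]

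With e = 30%:

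| p | Bi-26 arm | Difference | Share of positives without Bi-26 | Power at 177 per arm |
|---|---|---|---|---|
| 10% | 37% | 27 points | 19% | >99% |
| 30% | 51% | 21 points | 41% | 98% |
| 50% | 65% | 15 points | 54% | 82% |

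For p = 30%: 0.30 + 0.70 × 0.30 = 0.51; 0.51 − 0.30 = 0.21; 0.30 × 0.70 / 0.51 = 0.41.

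With e = 0 both arms read p, so the expected difference is 0 at any p. The arm's own proportion depends heavily on native carriage; the difference is a valid signal of a supplement effect.

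**Dose passage at Day 28.** Suppose e = 0, p = 30%, and dose material is detectable in a fraction t of dosed infants (assumed). The Bi-26 arm then reads 0.30 + 0.70t. That is 65% at t = 50% and 100% at t = 100%, against 30% on placebo, with no engraftment at all. Unlike at Day 56, here the between-arm difference is itself misleading.

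**Day 1 negatives.** The Day 1 sample precedes the first dose, so restricting to infants negative on Day 1 keeps the randomized comparison. If 30% were positive on Day 1, about 0.70 × 177 ≈ 124 per arm would remain. For the same pair of proportions the CI would be 1/√0.70 ≈ 1.20 times as wide.

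**The case against.** A reader might infer that the endpoint cannot show engraftment at all. The documents do not support that, for these reasons:

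- The stated objective concerns *B. infantis*, not the Bi-26 strain, and so does the pilot finding in Protocol 4.3. A subspecies-level readout fits both. This stands.
- Allocation is randomized and the placebo lacks *B. infantis*. A Day 56 or Day 90 difference in the mITT population can therefore show a persistent rise in carriage caused by the supplement, though not which strain persists. This stands, but the SAP does not plan that difference.
- The planned table lets a reader subtract the two proportions, and the listings would let someone find the Day 1 negatives. This is partly right. Such a comparison would be assembled afterwards, without a pre-specified visit or interval.
- Protocol 8.6 plans a Bi-26 measurement. It does, but that section leaves open testing all samples or only some. The exploratory stool samples stop at Day 56. Any further engraftment analyses are only potential, and SAP 6.2.2 places them outside the main study report.
- Protocol 4.2 reports markedly lower *B. infantis* abundance in severely malnourished Bangladeshi children. This is relevant, but it gives no prevalence for the present population. The uncertainty favours using the Day 1 result.

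A reader might also infer that a high Day 28 proportion would be reported as engraftment, or that a null weight result would be misread because of it. SAP 11.5.8 speaks of presence and makes no such claim. Non-persistence would be visible in the Day 56 and Day 90 columns.

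**Conclusion.** The point holds as a cheap improvement to a descriptive secondary endpoint. As planned, the Bi-26-arm proportion does not by itself measure engraftment. At Days 56 and 90 it includes native carriage: 19% to 54% of positives would carry no Bi-26 for native carriage of 10% to 50% and engraftment of 30%. At Day 28 it can also include dose passage, which the placebo arm cannot correct. The randomized contrast at Days 56 and 90 can answer the question at group level, but it is not planned.

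The carriage, engraftment and passage rates are illustrative assumptions, as are independence of native and supplemented carriage and 177 evaluable stools per arm. The visit timing rests on the documents' windows and on dosing that ends on Day 28. The documents do not describe the qPCR target. That the assay counts every *B. infantis* is the natural reading of the wording, not an established fact. The primary analysis and sample size are unaffected.

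**What to change.** In SAP 11.5.8 and Table 8, before unblinding:

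1. Name Day 56 as the engraftment time point and Day 90 as persistence.
2. Report the Bi-26 minus placebo difference in proportions with a 95% CI at both visits, overall and among infants negative on Day 1. Name the interval method.
3. Label the Day 28 result as detection during dosing.
4. Where Bi-26-specific results from Protocol 8.6 exist, show them alongside as supportive. No new assays are required.

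The cost is SAP wording and a few more table rows, from the same visits and samples. The Day 1-negative subset is smaller, so its CI will be wider for the same proportions. The by-arm proportions already planned can stay.

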11.5.9 Exploratory outcomes

Exploratory stool will be collected across enrollment, Day 28 and Day 56 visits and serum samples will be collected across enrollment and Day 28 visits. Further details on analysis of these outcomes will be discussed in an exploratory analysis plan.

11.5.10 Interim Analysis

No formal interim analysis is planned for this study.

11.6 Safety Analyses

All safety analyses will be performed for the Safety population.

11.6.1 Adverse Events

Safety assessments include SAEs and AEs from the time the ICF is signed through Day 90 (or at the date of last visit/study discontinuation).

An AE is considered treatment emergent if it started on or after the date of first dose of study intervention administration.

Confidential Page 37 of 50

An AE overview table containing the number and percentage (expressed in percent) of participants with AEs from Day 1 through Day 90 will be summarized by treatment group for the following:

- Any AE
- Any TEAE
- TEAEs related to study intervention
- TEAEs by maximum severity (Mild, Moderate and Severe)
- TEAEs leading to study intervention discontinuation
- TEAEs leading to study withdrawal
- Serious TEAEs
- Serious TEAEs with Outcome of Death

Additionally, the number and percentage of participants with AEs will be provided by SOC and PT and by treatment group for the following:

- Any TEAE
- TEAEs by maximum severity
- TEAEs related to study intervention
- Serious TEAEs
- Serious TEAEs related to study intervention

By-period summaries will be presented for TEAE and serious TEAEs by treatment group, where period is defined as in Section 10.1.

The overall AE summary table, AE table by SOC and PT and SAE table by SOC and PT will be presented by subgroups as specified in Section 8.2.

All AEs and SAEs will be classified according to the latest version of MedDRA.

SOC and PT will be sorted alphabetically by SOC and by decreasing frequency of preferred term in the all Bi-26 group (then alphabetically for ties). If a participant has more than one AE at a given level (eg, SOC and preferred term), the participant will only be counted once within that level. All summary tables will include the number of AEs. Missing severities and relationship will not be regarded as 'worst case'.

The following listings will be presented:

- All AEs through to Day 90
- SAEs through to Day 90

The AE listing by participant will display all reported AEs up to Day 90 and will include the verbatim term in addition to the SOC and preferred term. This listing will also include all relevant data associated with the event: eg, date of onset, date resolved, date of first dose, date of last dose, severity, whether AE is serious, outcome, relationship to study intervention, action taken with study intervention, and required therapy. When a date is presented, the study day

Confidential Page 38 of 50

associated with the date will also be displayed. The same listing will be presented for SAEs but will also include seriousness criteria.

11.6.2 **Deaths**

The death participant listing will include date and time of death, whether the condition under study contributed to death, primary cause of death and autopsy findings (if applicable).

